### Methods & Procedures:

We aim to compare stimulation parameters (frequency and amplitude, 1-ms pulses) using a monophasic waveform for different spinal segment sites to modulate BP. Sites for stimulation during a series of seated experiments will include 1) T 7/8; 2) T 9/10; 3) T11/12; and 4) L1/2, while beat-to-beat seated BP is continuously monitored and recorded in hypotensive individuals with SCI.

This study will take approximately 7-study visits, between 1-3 hours, per subject. Participants will be asked to arrive between 8:00 am and noon at the James J Peters VA Medical Center (JJP VAMC), after a normal breakfast and a good night sleep. The participants will be asked to not drink alcohol or caffeine 12 hours prior to their visit and there will be at least 3 days between study visits.

Approach: We will compare the electrode placement sites and amplitude during seated rest to modulate BP. We anticipate that BP responses will vary among the participants regarding the location of the electrode placement site and signal amplitude. Participants will visit the laboratory 8 times: visit 1): informed consent and medical intake to determine eligibility for enrollment in the study. Visits 2-8: amplitude (mA) mapping sessions at each electrode placement site (randomized), with continuous beat-to-beat BP monitoring at the finger arteriole and at 1-minute intervals at the brachial artery.

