In-person Interview, Consent Process and Eligibility determination and Orthostatic challenge without stimulation– Visit 1: Paperwork including consents and medical history will be conducted by the investigator for each participant. Participant eligibility will be determined by inclusion/exclusion criteria listed in the Human Subjects documentation. Cardiovascular systemic hemodynamics (heart rate and BP) will be measured in the seated position for 5 minutes. The participant will then lie down in the supine position for 10 minutes prior to collecting pulse wave velocity at the carotid and femoral artery. A blood sample of renin, aldosterone and NE will be drawn and continuous beat-to-beat heart rate, BP and CBFv will be recorded for 5 minutes. Participants will then be secured to a tilt table and will be tilted to 30°, 45° and 60° for 10 minutes at each angle with continuous beat-to-beat monitoring of the systemic hemodynamics. A second blood draw of renin, aldosterone and NE will be drawn at the end of 10 minutes at 60° tilt (**Table 2**). Participants will be deemed eligible for the TSCS mapping if their BP response to the head-up tilt maneuver meets the definition of orthostatic hypotension. A six-item validated orthostatic hypotension questionnaire will be used during the orthostatic tilt visits to report associated symptoms (54) (**Appendix**). Participants will undergo response to stimulation prior to entry to study and will be monitored for suitability to study protocol by [name] prior to stimulation.

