Amplitude Parameter Mapping Visits 2-8: Before TSCS, electrodes will be placed on the vertebral midline at the spinous process (T7/8, T9/10, T11/12, L1/2), and the active site will be randomized. Each visit, we will complete one electrode placement site. Amplitude ramping will start at 10mA, with 10mA increments (pulse width, 1ms, frequency 30 Hz as shown (13)). Continuous real-time BP and heart rate will be measured for 5-minutes, before, during and after stimulation. During ramping, amplitude will stop increasing when SBP reaches optimal SBP between 110-120 mmHg (100-120 mmHg females) or reaches 100 mA with no SBP response (see below TSCS decision Tree). Amplitude will be decreased in 10 mA decrements in stimulation. BP will be continuously recorded during the rest period. Bilateral muscle activation (rectus femoris, medial hamstring, and gastrocnemius) will be monitored during all experiments to determine if skeletal muscle contractions are contributing to increases in BP. Additionally, signs and symptoms of autonomic dysreflexia will be monitored during TSCS testing in visits 3-6 by a questionnaire (**Appendix**). After every incremental increase of amplitude, investigator will ask participant if he/she is experiencing any symptoms. Maximum ramping amplitude will be 100 mA and testing will be halted if participant experiences any discomfort during testing. Based on preliminary work, regulation of neuromodulation of BP will occur at stimulation levels less than 100mA.

Participants will be notified by investigator if any of the findings from this study will affect the participants' health or welfare.

- Cardiovascular Assessments: While the subject is seated 3 ECG electrodes will be affixed to the chest and abdomen for continuous monitoring of HR and respiration rate (RR). Brachial BP will be monitored at 1 minute intervals using a standard adult BP cuff placed at the right upper arm, and beat-to-beat finger arteriolar BP will be continuously monitored from the right

middle finger throughout testing. Mean arterial pressure (mmHg) will be calculated from brachial BP using the formula: [systolic BP + (2\* diastolic BP)]/3. Beat-to-beat HR, RR and BP data will be viewed in real-time and stored for subsequent analysis using customized programs created with LabView graphical software.

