- Transcutaneous spinal cord stimulation: Digitimer DS7A will be used to provide constant current voltage of electrical activity during the mapping and final orthostatic challenge. TSCS electrodes at different sites on the spinal process (T7/8, T9/10, T11/12, L1/2) and various amplitudes and frequencies will be assessed to determine the optimal site to increase blood pressure and decrease symptoms of orthostatic hypotension.

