### **Study Compensation:**

Participants will be given a study compensation of \$100 for each study visit (9 total visits); participants could earn a total of \$900 for completing all study visits.

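### The dysreflexia questionnaire is tied to visits 3-6, but mapping is labelled visits 2-8 and the stimulated tilt has no visit number, so the form can miss up to three mapping visits

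*Protocol*

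**What the plan says.** **Visit totals.** The protocol's Methods & Procedures section first says "This study will take approximately 7-study visits, between 1-3 hours, per subject", and shortly afterwards "Participants will visit the laboratory 8 times". The Study Compensation section pays "for each study visit (9 total visits").

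**Mapping visits.** The Approach paragraph and the heading of the amplitude mapping section both label visits 2-8 as mapping. There are four electrode sites (T7/8, T9/10, T11/12, L1/2), in randomized order, and "Each visit, we will complete one electrode placement site".

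**Dysreflexia form.** Within that mapping section, "signs and symptoms of autonomic dysreflexia will be monitored during TSCS testing in visits 3-6 by a questionnaire".

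**Other stimulated sessions.** The Visit 1 paragraph, whose heading describes an orthostatic challenge without stimulation, ends by saying "Participants will undergo response to stimulation prior to entry to study". The stimulator paragraph says the device is used "during the mapping and final orthostatic challenge", and the Abstract confirms a tilt under stimulation after mapping. Neither session has a visit number. The form named for tilt visits is a different one: "A six-item validated orthostatic hypotension questionnaire will be used during the orthostatic tilt visits to report associated symptoms".

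**Risk.** Inclusion is limited to injuries at or above T6, and Risk and Discomforts lists autonomic dysreflexia among the possible effects of stimulation.

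**The concern.** The protocol chose a structured form for a risk it names, then tied that form to visit numbers that do not match its own schedule. Staff following the text cannot tell whether the form is due at visits 2, 7 and 8, at the stimulated tilt, or at the test before entry. Under the literal reading the first mapping exposure, visit 2, is among those missed.

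Because site order is randomized, an uncovered visit falls on different sites in different participants. Dysreflexia symptoms then cannot be tabulated on the same basis across sites, currents and the stimulated tilt. With 12 participants there is little room to lose part of the safety record.

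**Working it through.** This is a count from the visit numbers in the protocol; no power or alpha figure is involved.

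**1. The visit total.** Visit 1 plus visits 2-8 gives 1 + 7 = 8. This reproduces the stated total of 8, but not about 7 or 9.

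**2. Mapping visits needed.** Four sites at one site per visit need 4 visits. The label 2-8 supplies 7, so three numbered mapping visits have no stated site.

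**3. Mapping visits without the form.** The form covers {3, 4, 5, 6}. The gap is the set of mapping visits minus that set.

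| Reading of the schedule | Mapping visits | Without the form | Share |
|---|---|---|---|
| As written | 2-8 | 2, 7, 8 | 3/7 = 43% |
| Four visits from visit 2 | 2-5 | 2 | 1/4 = 25% |
| Four visits from visit 3 | 3-6 | none | 0/4 = 0% |
| Four visits ending at visit 8 | 5-8 | 7, 8 | 2/4 = 50% |

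Only the first row is the printed schedule; the others are assumptions. The number missed runs from 0 to 3 per participant, and 3 is the upper bound.

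**4. Across the trial, as written.** 12 participants × 7 mapping visits = 84 participant-visits. The form covers 12 × 4 = 48, leaving 12 × 3 = 36 without it.

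**5. Stimulated sessions without a number.** In the 8-visit schedule, visit 1 is the unstimulated tilt and visits 2-8 are all mapping, so there is no slot for the stimulated tilt. Up to two further sessions (the test before entry and the stimulated tilt) therefore have no dysreflexia form clearly assigned. They should not simply be added to the three above: if the test before entry is in fact visit 2, it would be counted twice.

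**The case against.** The strongest reply is that visits 3-6 are exactly four visits, matching four sites at one per visit. A coherent schedule can be built around them: visit 1 for screening and the unstimulated tilt, visit 2 for the stimulation check, visits 3-6 for mapping, and visit 7 for the stimulated tilt. That totals 7, in line with one of the stated totals, and no mapping visit lacks the form. The window may be left over from such a schedule. This is plausible, and it is why the lower bound is 0. But it is an inference that contradicts the 2-8 label, which is printed in two places, and it still leaves the stimulation check and the stimulated tilt outside visits 3-6.

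The sentence about stimulation before entry is also unclear. It may not describe a separate session; the test could sit within visit 1 or be visit 2. That stands, and the count of extra sessions is therefore given as up to two. In either position it falls outside visits 3-6.

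Safeguards remain. At mapping visits, blood pressure and heart rate are recorded continuously, brachial pressure is taken every minute, symptoms are asked about after each current step, and discomfort halts testing. Risk and Discomforts, which is not limited to mapping, stops stimulation if a listed risk occurs and has a physician present during testing. This limits the point to structured capture; it is not a loss of surveillance. The question asked at each step covers symptoms in general, with no stated dysreflexia items or scale, so it does not replace the form.

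Neither document names a dysreflexia endpoint or a planned comparison of dysreflexia between sessions, and the systolic pressure analysis and its power are unaffected. That keeps the severity moderate. The Appendix and Table 2 were not in the text reviewed and could hold further instructions, but they would not remove the explicit visit window or reconcile the three totals.

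**Conclusion.** The concern holds. The visit schedule contradicts itself, and the rule for the dysreflexia form inherits the contradiction. As printed, the form is missed at 3 of 7 mapping visits per participant. Allowing for other schedules, the number is 0 to 3, and reaching 0 requires a schedule that the protocol does not state. In addition, up to two stimulated sessions without a visit number have no dysreflexia form clearly assigned, and for the stimulated tilt this is true whichever mapping schedule was meant.

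The numbering conflict is certain. The exact number of missed visits depends on which schedule was intended and on what the unseen Appendix and Table 2 contain. This should be corrected because it concerns a named risk in a population selected at or above T6, but it does not alter the primary analysis.

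**What to change.** In the mapping section, replace the restriction to visits 3-6 with a requirement that the dysreflexia questionnaire be completed at every session in which stimulation is delivered, and name the stimulation test before entry and the final stimulated tilt explicitly. This works under any intended schedule.

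Then settle one visit schedule and carry it through Methods & Procedures, the Visit 1 paragraph, the mapping section, the stimulator paragraph and Study Compensation. State how many mapping visits there are and what each is for, where the test before entry falls, and which visit number the stimulated tilt has.

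The cost is protocol wording plus a short existing form at up to three more mapping visits, the test before entry and the tilt. On the printed schedule, coverage of mapping visits would rise from 48 to 84 of 84 participant-visits.

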**1. Intolerable to patient**

- a. If uncomfortable, but tolerable, lower increments to 5mA increase/interval

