**2. Sustained BP response - 3 or more manual systolic BP within the target range:**

**MALES: systolic BP 110-120 mmHg; FEMALES: systolic BP 100-120 mmHg**

- a. At each mA interval a manual blood pressure is taken ~1 minute:
  - i. **IF:** systolic BP increases by 10 mmHg above baseline repeat BP recording
  - ii. **IF:** still 10 mmHg above baseline take a third BP recording.
  - iii. **IF:** still 10 mmHg - but < 100 mmHg (< 90 females mmHg) increase by 10 mA and repeat manual BP assessments.
  - iv. **IF:** still 10 mmHg - but < 110 mmHg (< 100 mmHg females) increase by 5 mA and repeat manual BP assessment.
  - v. **IF:** between 110-120 mmHg (100-120 mmHg females) stop intensity ramp and monitor BP for 10 minutes at that mA ramp.
  - vi. **IF:** only 1 or 2 readings that are 10 mmHg above baseline continue incremental ramp at 10 mA.
  - vii. **IF:** during the 10-minute assessment systolic BP drifts down to < 110 but > 100, continue ramp at 5 mA.
  - viii. **IF:** during the 10-minute assessment systolic BP drifts down to < 100, continue ramp at 10 mA.

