**3. Reach a stimulation intensity of 100 mA without a blood pressure response or intolerable symptoms.**

### **Risk and Discomforts:**

- Heart Rate, Arterial Stiffness and Blood Pressure: These are non-invasive procedures that involve minimal risk; however, some participants may experience discomfort when the ECG electrodes are removed from the skin and when the blood pressure cuffs are inflated.
- Transcutaneous stimulation: Participants may get headaches, autonomic dysreflexia, skin breakdown at the electrode placement site, pain, severe contractures (fractures) and muscle tears. If any of these potential risks occur, the stimulation will cease immediately and the investigators will monitor the situation.

As with any research, there may be unforeseen risks and discomforts. [name], a medical doctor associated with the study, will be available and present during testing to for clinical intervention if necessary or to treat any medical emergency.

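### Two stimulation dosing rules conflict as written: tolerable discomfort both halts and continues the ramp, and the hold rules lack female cut-offs, so a woman drifting from 110 mmHg or more to 101–109 gets 5 mA more while in target

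*Protocol*

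**What the plan says.** **Discomfort.** The Protocol gives three instructions.

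- Methods & Procedures, Amplitude Parameter Mapping: "testing will be halted if participant experiences any discomfort during testing".
- TSCS Blood Pressure decision tree, item 1: the ramp ends when stimulation is "Intolerable to patient". Item 1a adds: "If uncomfortable, but tolerable, lower increments to 5mA increase/interval".
- Risk and Discomforts: stimulation ceases at once for headache, autonomic dysreflexia, skin breakdown, pain, contractures or muscle tears.

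The mapping text refers to the tree only in its sentence on the blood pressure target and the 100 mA ceiling. It makes no such reference for discomfort.

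**Blood pressure target and hold.** The tree's target line is sex-specific: "MALES: systolic BP 110-120 mmHg; FEMALES: systolic BP 100-120 mmHg". The mapping text and rule v repeat the female range. Ramp rules iii and iv also give female values: "still 10 mmHg - but < 100 mmHg (< 90 females mmHg) increase by 10 mA and repeat manual BP assessments" and "still 10 mmHg - but < 110 mmHg (< 100 mmHg females) increase by 5 mA and repeat manual BP assessment". Rule v then stops the ramp and starts a 10-minute hold.

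Rules vii and viii govern that hold, and each gives one set of numbers for everyone. Under rule vii, a downward drift to below 110 but above 100 mmHg resumes the ramp by 5 mA. Under rule viii, a drift to below 100 mmHg resumes it by 10 mA. These are the male cut-offs of rules iii and iv.

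**The concern.** The mapping procedure is the intervention in this study, so its stop and step rules are dosing instructions.

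On discomfort, one participant report leads to opposite actions. An operator following the mapping text ends testing; an operator following the tree keeps raising the current. The investigator must ask about symptoms after every increment, so the choice can arise at any step. Ending some sessions early and continuing others also makes the sites less comparable.

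On the hold, the written rule orders more current for some women whose pressure already meets the protocol's own goal. The study aims at an individual map of stimulation settings. An unneeded step could therefore raise the current recorded for a woman.

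**Working it through.** There is no stated figure to reproduce. The check sets the rules side by side and enumerates whole-mmHg values.

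**1. Discomfort**

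| Participant's state | Mapping text | Decision tree item 1/1a | Risk and Discomforts |
|---|---|---|---|
| Tolerable discomfort, no listed event | Halt | Continue, 5 mA steps | Silent |
| Listed event (such as pain, headache, dysreflexia) | Halt if it is felt as discomfort | Depends on tolerability | Stop |
| Intolerable | Halt | Stop | Stop if a listed event |

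The first row is the contradiction that nothing resolves. In the second row the risk section gives a clear stop. In the third, the mapping text and the tree agree.

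Item 3 of the tree ("Reach a stimulation intensity of 100 mA without a blood pressure response or intolerable symptoms") adds little. Its natural reading is a ceiling rule, reaching 100 mA with neither a response nor intolerable symptoms, so only item 1 clearly stops for intolerability.

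**2. Hold phase, women**

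Inputs: the female target of 100–120 (target line, rule v); rules vii and viii as written; rules iii and iv for comparison.

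| SBP after downward drift (mmHg) | In female target? | Rules vii/viii as written | What the target or ramp rules imply |
|---|---|---|---|
| 110–120 | Yes | No increase | No increase |
| 101–109 | Yes | +5 mA (vii) | No increase |
| 100 | Yes | Neither rule applies | No increase |
| 90–99 | No | +10 mA (viii) | +5 mA under rule iv, if at least 10 above baseline |
| Below 90 | No | +10 mA (viii) | +10 mA |

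- Whole values in the female target: 120 − 100 + 1 = 21.
- In-target values that trigger an increase: 109 − 101 + 1 = 9, so 9 of 21.
- The target has no baseline condition, so these nine conflict at any baseline.

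Rule vii is worded as a drift down to below 110. It therefore clearly covers a woman who was at 110 or more and falls to 101–109, for example from 112 to 105. For a woman who enters the hold at 101–109 and stays there, the wording is ambiguous.

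At 90–99 the woman is below target and more current is intended, so only the step size differs. Rule iv needs SBP of at least baseline + 10. The number of differing whole values is max(0, min(10, 90 − baseline)): 10 at a baseline of 80, 5 at 85, 1 at 89 and 0 at 90 or more. These baselines are assumed; the documents give no distribution.

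**3. Hold phase, men**

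No value in 110–120 triggers an increase. At exactly 100 mmHg neither rule applies, because vii needs more than 100 and viii less than 100.

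**4. After the amendment**

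With female cut-offs in rule vii (below 100 but at least 90) and rule viii (below 90), in-target female values that trigger an increase fall from 9 to 0. Writing the male lower bound of rule vii as at least 100 closes the gap for men.

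**The case against.** The best defence is that trained operators would manage. The female target appears three times, rules vii and viii sit beneath the target line, and rules iii to v show which female values were meant. A physician is present during testing. This makes harm less likely, but the written rule still orders a different action, and an operator cannot tell an omission from an intention. The physician's presence does not settle which discomfort rule applies.

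Four stronger readings are tempting, and the documents do not support them.

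- *Any woman in target gets more current.* Rule vii clearly reaches only those who fall from 110 or above to 101–109.
- *The discomfort conflict leaves participants exposed to autonomic dysreflexia.* Dysreflexia is itself an immediate-stop event, symptoms are asked about after each increment, and a dysreflexia questionnaire is used at visits 3 to 6.
- *Rule viii overdoses women at 90–99 mmHg.* They are below target, and nothing requires hold steps to equal ramp steps.
- *The optimal current, and so the SAP's individual effect sizes, will be biased upwards.* The documents do not say how a participant's optimum is chosen or that it is the last current held. The SAP's mixed model takes current as a fixed effect, so an extra step would be one more observed level.

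**Conclusion.** Both contradictions stand on the text, and both should be fixed.

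1. Tolerable discomfort outside the listed stop events has two opposite instructions and no stated precedence.
2. A woman who drifts from 110 mmHg or more to 101–109 during the hold is ordered 5 mA more while inside her target. That band is nine of the 21 whole values in her range.

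The missing female cut-off in rule viii (a step-size inconsistency) and the uncovered value of 100 mmHg in men are lesser defects of the same rules.

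The size is known only per trigger: 5 mA under rule vii. The number of women, the frequency of drift and the frequency of tolerable discomfort are not given, so neither the total shift in recorded current nor any effect on the SAP analysis can be stated. No power or sample-size figure is affected. The conclusion assumes that rules vii and viii are applied literally and that the female target of 100–120 mmHg is the intended one.

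**What to change.** **Discomfort.** Use one rule in both places. Either:

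- change the mapping sentence so that tolerable discomfort continues in 5 mA steps, while intolerable discomfort or any event listed under Risk and Discomforts stops stimulation; or
- delete item 1a, if the clinicians want any discomfort to halt testing.

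If the first option is chosen, add a line saying how the operator separates tolerable discomfort from pain, since pain is a listed stop event.

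**Hold rules.**

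- Rule vii, resume by 5 mA: men below 110 but at least 100 mmHg; women below 100 but at least 90 mmHg.
- Rule viii, resume by 10 mA: men below 100 mmHg; women below 90 mmHg.
- State that a woman who is within 100–120 mmHg during the hold gets no increase.

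**Cost.** A short protocol amendment to one sentence (or item 1a) and two rules. It needs no new visits, participants or equipment and no SAP change.

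### The brachial cuff and the finger BP sensor are both on the right arm, so each cuff inflation interrupts the beat-to-beat systolic trace

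*Protocol*

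**What the plan says.** The protocol's Methods & Procedures plans the mapping visits (2 to 8) "with continuous beat-to-beat BP monitoring at the finger arteriole and at 1-minute intervals at the brachial artery", so both devices run together.

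Cardiovascular Assessments gives the placement. For the cuff: "Brachial BP will be monitored at 1 minute intervals using a standard adult BP cuff placed at the right upper arm". For the finger sensor: "beat-to-beat finger arteriolar BP will be continuously monitored from the right", and after a page break the sentence continues "middle finger throughout testing".

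On recording, the section on mapping visits says: "Continuous real-time BP and heart rate will be measured for 5-minutes, before, during and after stimulation". On use of the data: "Beat-to-beat HR, RR and BP data will be viewed in real-time and stored for subsequent analysis".

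The decision tree works from a different source: "At each mA interval a manual blood pressure is taken ~1 minute". Mean arterial pressure is computed from the brachial readings.

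The SAP makes systolic BP the primary outcome and does not say whether the finger device or the cuff supplies it. Neither document moves a device to the other arm, pauses the finger recording, or flags or removes beats recorded while the cuff is inflated.

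**The concern.** The finger lies downstream of the cuff. While the cuff is above systolic pressure, no pulse reaches the finger, and the waveform needs some time to return after deflation. This is general physiology and is not stated in the documents. With readings every minute, the finger record becomes a series of segments with a gap or a false low in each cycle.

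Two things are at stake. Valid beats are lost and no later analysis can recover them; masking only discards the bad ones. If the affected beats are not masked, they enter any summary of beat-to-beat systolic BP as low values unrelated to stimulation. The beat-to-beat record is stored for analysis, and the SAP bases its power statement on the number of repeated systolic readings per participant. The finger trace is therefore a possible source of the primary outcome, though not a confirmed one.

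**Working it through.** The plan states no figure for this point, so there is none to reproduce. The check has two parts.

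**Placement**

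| Item | Cuff | Finger sensor |
|---|---|---|
| Side | right upper arm | right middle finger |
| Timing | every minute | throughout testing |
| Visits | 2 to 8 | 2 to 8 |

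The sides match and the times overlap, so the conflict follows from the text itself.

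**Share of finger signal lost**

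Inputs from the protocol: one cuff reading per 60 s; 5-minute recording windows; a 10-minute hold once the target range is reached (decision tree). Assumed input: *t*, the seconds from the start of inflation until the waveform recovers, taken as 15 to 45 s.

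Share of each minute lost = *t*/60. Loss in a 5-minute window = 5 × *t*. Loss in the 10-minute hold = 10 × *t*.

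| *t* (assumed) | Share of each minute | Of a 300 s window | Of the 600 s hold |
|---|---|---|---|
| 15 s | 15/60 = 25% | 75 s | 150 s |
| 20 s | 20/60 = 33% | 100 s | 200 s |
| 30 s | 30/60 = 50% | 150 s | 300 s |
| 45 s | 45/60 = 75% | 225 s | 450 s |

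The share is given per minute with a reading, not per current step. The decision tree's one-minute figure says when a BP is taken and does not fix the length of a step.

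**Effect if affected beats are left in**

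Let a share *f* of beats read *d* mmHg low. The mean falls by *f* × *d*. The added SD is *d* × √(*f*(1 − *f*)). The error in a stimulation-minus-baseline difference is −*d* × (*f*_stim − *f*_base). With equal cuff timing in both periods the last term is zero, but the added SD remains.

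Cuff timing need not be equal. The decision tree asks for a second and third reading after a 10 mmHg rise. Suppose these are additional to the one-minute schedule, which the protocol does not settle. At *t* = 15 s, two readings in a minute take 30/60 = 50% against 25% at baseline, and the difference is biased by −0.25 × *d*, against the settings that produced a response. The documents give no value for *d*, so no figure in mmHg follows.

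**The case against.** The strongest reply is that the trial's decisions do not rest on the finger trace. This stands. The decision tree uses manual readings, taken here to be the brachial cuff readings, and mean arterial pressure is brachial. Neither is touched by a gap in the finger signal. If the sponsor confirms that the primary systolic BP also comes from the cuff, the primary analysis is untouched as well.

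A second reply is that the planned analysis is a contrast: responses are compared with baseline, and current is modelled from 0 mA. An artefact of similar size in both periods would largely cancel in the mean difference. This also stands, with two limits. The added variance does not cancel, and it would shrink a Cohen's d that uses a beat-level SD. The extra readings after a response could also make cuff timing unequal.

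A third reply is that full occlusion mainly gives a flat or missing waveform that staff would see and remove. That is plausible, but no rule says so, and removal still loses the data.

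Two stronger readings are tempting, and the documents do not support them:

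- A reader might suppose that a third of beats read 30 mmHg low, obtain a 10 mmHg error, and set it against the decision tree's 10 mmHg response criterion. The 30 mmHg is hypothetical, and that criterion is applied to manual readings, so finger artefact cannot trigger or hide a response there.
- A reader might infer that safety monitoring fails during inflation. At that moment the cuff is itself taking a BP. ECG monitoring is continuous, symptoms are asked about after each increment, and a physician is present during testing.

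**Conclusion.** The point holds as a measurement conflict that should be fixed. With both devices on the right arm, the beat-to-beat systolic BP cannot be continuous as the protocol requires. Under an assumed 15 to 45 s per inflation and recovery, 25% to 75% of each minute with a reading has no valid finger BP.

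The certain consequence is lost data. Added noise follows only if affected beats are kept, and bias only if, in addition, cuff timing differs between baseline and stimulation. Whether any of this reaches the primary analysis depends on the device that supplies systolic BP, which the SAP leaves open. The documents do not support a claim that the primary result is wrong by a stated amount.

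**What to change.** 1. In Cardiovascular Assessments, put the brachial cuff on the arm opposite the finger sensor and keep the same sides for each participant at every visit.
2. Where only one arm is usable, exclude finger beats from the start of each inflation until the waveform has recovered, before any systolic BP is computed. Apply the same rule to any recordings already made with both devices on one arm.
3. In the SAP, name the device that supplies the primary systolic BP.

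The cost is a line or two in the protocol and one in the SAP. No extra equipment, staff or visit time is needed, and the stimulation procedure does not change.
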